8.4 Exploratory or Other Analyses

8.4.1 Exploratory Endpoint Analyses

•	
•	
•	
•	
•	
•	
•	
•	
•	
•	
•	
•	
•	
•	
•	

8.4.2 Other Analyses

The CMAI total score, CMAI subscales (Aggressive Behavior, Physically Nonaggressive Behavior, and Verbally Agitated Behavior), CGI-S, CGI-I,

at

each time point will be analyzed in the same manner as for the primary and secondary efficacy endpoints and the exploratory endpoints. Descriptive statistics or frequency distribution of actual measurements and changes from baseline at each time point will be calculated by treatment group.

9 Safety Analyses

Safety analysis will be performed using the safety analysis set. Baseline is defined as the last data obtained prior to initiation of IMP treatment.

9.1 Extent of Exposure

Descriptive statistics and frequency distribution (1-7, 8-14, 15-21, 22-28, 29-35, 36-42, 43-49, 50-56, 57-63, 64-70, > 70 and ≥ 7 , ≥ 14 , ≥ 28 , ≥ 42 , ≥ 56 , ≥ 70) of the duration (days) of treatment with the IMP will be determined for each treatment group and for the overall brexpiprazole group.

9.2 Adverse Events

Adverse events will be coded using Medical Dictionary for Regulatory Activities (MedDRA) (Ver. 25.0). The incidences of the following events will be summarized according to System Organ Class (SOC) and Preferred Term (PT) for each treatment group and for the overall brexpiprazole group. If an AE occurs more than once in the same subject, the severest event will be used in summarization.

- Adverse events occurring after initiation of IMP administration (treatment-emergent adverse events [TEAEs])
- TEAEs by severity
- TEAEs with an outcome of death
- Serious TEAEs
- TEAEs leading to discontinuation of the IMP
- TEAEs occurring in $\geq 2\%$ of subjects in any brexpiprazole group and more frequently than in the placebo group
- TEAEs by days of initial onset (1-7, 8-14, 15-21, 22-28, 29-35, 36-42, 43-49, 50-56, 57-63, 64-70, > 70, post-trial treatment).

TEAEs potentially causally related to the IMP will also be summarized in the same manner.

9.2.1 Adverse Events of Interest

Each AE of interest is defined in Appendix 4. Numbers and proportions of subjects with the following AEs of interest will be summarized by SOC and PT for each treatment group and for the overall brexpiprazole group.

- Extrapyramidal AEs
- Accident- and injury-related AEs
- Cerebrovascular AEs
- Cardiovascular AEs
- Glucose metabolism-related AEs
- Lipid metabolism-related AEs
- Body weight-related AEs
- Blood disorder-related AEs
- Hypersensitive symptom-related AEs
- Neuroleptic malignant syndrome-related AEs
- Orthostatic disorder-related AEs
- Prolactin increase-related AEs
- QT interval prolongation-related AEs
- Rhabdomyolysis
- Seizure-related AEs
- Oversedation-related AEs
- Suicide/suicide attempt-related AEs
- Venous thrombosis
- Pneumonia-related AEs

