2.1 Trial Rationale

It is considered that neurotransmitters such as serotonin, dopamine and noradrenaline are involved in agitation. Brexpiprazole, which regulates the serotonin-dopaminergic system, is expected to improve agitation in patients with dementia of the Alzheimer's type while suppressing expression of extrapyramidal symptoms.

Based on the results of the 2 overseas confirmatory trials in agitation associated with dementia of the Alzheimer's type (Trial 331-12-283 and Trial 331-12-284), and because

the PK of brexpiprazole is not affected by ethnicity, it is considered that brexpiprazole will also show efficacy in Japanese patients with agitation associated with dementia of the Alzheimer's type.

In the overall population of Trial 331-12-284, no statistically significant differences were noted in the flexible-dose brexpiprazole group compared with the placebo group, but the results of an additional analysis showed the efficacy of brexpiprazole in patients with aggression.

On the basis of these findings, a multicenter, placebo-controlled, randomized, doubleblind, parallel-group comparison trial to verify the superiority of brexpiprazole over placebo, evaluate the safety of brexpiprazole, and confirm an optimal dose in Japanese patients with aggression in agitation associated with dementia of the Alzheimer's type was planned. The doses of brexpiprazole were determined with reference to the data of the 2 overseas trials, and two doses were selected: a dose of 2 mg, which showed a statistically significant improvement compared with the placebo group in Trial 331-12-283 and might be an optimal dose in Japanese patients, and a dose of 1 mg to obtain the dose-response relationship in Japanese patients. Duration of treatment was set to 10 weeks.

Furthermore, on the basis of the report¹⁹ of the risk of death associated with atypical antipsychotics, criteria to exclude patients at high risk of cerebrovascular disorder, cardiac disorder, pneumonia, and other infections, which were the causes of death associated with atypical antipsychotics, were established to minimize the risk to subjects during the trial and an Independent Data Monitoring Committee (IDMC) was established to monitor safety during the trial, as measures to ensure subject safety.

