Vascular injury

Vascular rupture

Vena cava injury

Venous injury

Ventricle rupture

Vessel puncture site injury

Vitreous detachment

Vitreous injury

Vitreous loss

Vitreous prolapse

Vth nerve injury

Vulvovaginal injury

Wound

Wrist fracture

XIIth nerve injury

XIth nerve injury

Accelerated idioventricular rhythm

Version: 1.0 Date: 01/06/2023

Accessory cardiac pathway

Acute cardiac event

Acute cardiac event

Acute coronary syndrome

Acute left ventricular failure

Acute myocardial infarction

Acute pulmonary oedema

Acute right ventricular failure

Adams-Stokes syndrome

Agonal rhythm

Andersen-Tawil syndrome

Angina pectoris

Angina unstable

Angina unstable

Anginal equivalent

Anomalous atrioventricular excitation

Arrhythmia

Arrhythmia neonatal

Arrhythmia supraventricular

Arrhythmic storm

Arrhythmogenic right ventricular dysplasia

Arteriosclerosis coronary artery

Arteriospasm coronary

Atrial conduction time prolongation

Atrial escape rhythm

Atrial escape rhythm

Atrial fibrillation

Atrial flutter

Atrial parasystole

Atrial standstill

Atrial tachycardia

Atrioventricular block

Atrioventricular block complete

Atrioventricular block first degree

Atrioventricular block second degree

Atrioventricular conduction time shortened

Atrioventricular dissociation

Atrioventricular node dispersion

Atrioventricular node dysfunction

BRASH syndrome

Bifascicular block

Blood creatine phosphokinase MB abnormal

Blood creatine phosphokinase MB increased

Blood creatine phosphokinase abnormal

Blood creatine phosphokinase increased

Bradyarrhythmia

Brugada syndrome

Brugada syndrome

Bundle branch block

Bundle branch block bilateral

Bundle branch block left

Bundle branch block right

Cardiac asthma

Cardiac failure

Cardiac failure acute

Cardiac failure chronic

Cardiac failure congestive

Cardiac failure high output

Cardiac fibrillation

Cardiac fibrillation

Cardiac flutter

Cardiac perfusion defect

Cardiac ventricular scarring

Version: 1.0 Date: 01/06/2023

Cardiogenic shock

Cardiohepatic syndrome

Cardiopulmonary failure

Cardiorenal syndrome

Chronic atrial and intestinal dysrhythmia syndrome

Chronic coronary syndrome

Chronic left ventricular failure

Chronic right ventricular failure

Chronotropic incompetence

Conduction disorder

Congenital supraventricular tachycardia

Congestive hepatopathy

Cor pulmonale

Cor pulmonale acute

Cor pulmonale chronic

Coronary angioplasty

Coronary arterial stent insertion

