NEUROLEPTIC MALIGNANT SYNDROME Altered state of consciousness

Autonomic nervous system imbalance

Blood creatine phosphokinase MM increased

Version: 1.0 Date: 01/06/2023

Blood creatine phosphokinase abnormal

Blood creatine phosphokinase increased

Blood pressure abnormal

Blood pressure decreased

Blood pressure fluctuation

Blood pressure increased

Body temperature increased

Cardiovascular insufficiency

Catatonia

Coma

Confusional state

Consciousness fluctuating

Delirium

Depressed level of consciousness

Disorientation

Dyskinesia

Dyslalia

Dysphagia

Dystonia

Dystonic tremor

Extrapyramidal disorder

Fatigue

Freezing phenomenon

Heart rate abnormal

Heart rate increased

Hyperhidrosis

Hyperkinesia

Hyperpyrexia

Hypertension

Hyperthermia malignant

Hypertonia

Hyporesponsive to stimuli

Hypotension

Labile blood pressure

Labile hypertension

Leukocytosis

Loss of consciousness

Malignant catatonia

Muscle enzyme increased

Muscle necrosis

Muscle rigidity

Muscular weakness

Myalgia

Myoclonus

Myoglobin blood increased

Myoglobin blood present

Myoglobin urine present

Myoglobinaemia

Myoglobinuria

Necrotising myositis

Neuroleptic malignant syndrome

Oculogyric crisis

Opisthotonus

Palpitations

Parkinson's disease

Parkinsonian crisis

Parkinsonian rest tremor

Parkinsonism

Pyrexia

Respiratory failure

Resting tremor

Rhabdomyolysis

Salivary hypersecretion

Version: 1.0 Date: 01/06/2023

Serotonin syndrome Slow response to stimuli

Stupor Tachycardia Tremor

Unresponsive to stimuli Urinary retention

White blood cell count abnormal White blood cell count increased

Withdrawal catatonia

ORTHOSTATIC HYPOTENSION, DIZZINESS, AND SYNCOPE

Dizziness

Dizziness postural Hypotension

Orthostatic hypotension

Presyncope Syncope

PROLACTIN Amenorrhoea

Amenorrhoea-galactorrhoea syndrome

Anorgasmia Blood prolactin

Blood prolactin abnormal Blood prolactin increased

Breast discharge
Breast enlargement
Breast swelling
Ejaculation disorder
Erectile dysfunction
Female orgasmic disorder
Female sexual dysfunction

Galactorrhoea Gynaecomastia Hirsutism

Hyperprolactinaemia Hypomenorrhoea Lactation disorder Libido decreased Loss of libido

Male sexual dysfunction Menstrual disorder Menstruation delayed Menstruation irregular Oligomenorrhoea Orgasm abnormal

Orgasmic sensation decreased Prolactin-producing pituitary tumour

Sexual dysfunction Arrhythmic storm Cardiac arrest

Cardiac death
Cardiac fibrillation
Cardio-respiratory arrest

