CT 0.7.1	System Organ Class and Preferred Term (Safety Analysis Set)
CT-8.7.1	Incidence of TEAEs of at Least 2% in Any Brex Group and Greater Than Placebo
CT-8.7.2	by MedDRA System Organ Class and Preferred Term (Safety Analysis Set) Incidence of Drug-related TEAEs of at Least 2% in Any Brex Group and Greater
C1-6.7.2	Than Placebo by MedDRA System Organ Class and Preferred Term (Safety
	Analysis Set)
CT-8.8.1	Incidence of TEAEs by MedDRA System Organ Class, Preferred Term and Time to
0.0	First Onset (Safety Analysis Set)
CT-8.8.2	Incidence of Drug-related TEAEs by MedDRA System Organ Class, Preferred Term
	and Time to First Onset (Safety Analysis Set)
CT-8.9.1	Incidence of TEAEs for EPS (Safety Analysis Set)
CT-8.9.2	Incidence of TEAEs for Accidents and Injuries Including Fall (Safety Analysis Set)
CT-8.9.3	Incidence of TEAEs for Cerebrovascular Events (Safety Analysis Set)
CT-8.9.4	Incidence of TEAEs for Cardiovascular Events (Safety Analysis Set)
	· · · · · · · · · · · · · · · · · · ·

CT-8.9.5	Incidence of TEAEs for Effect on Glucose (Safety Analysis Set)
CT-8.9.6	Incidence of TEAEs for Effect on Lipids (Safety Analysis Set)
CT-8.9.7	Incidence of TEAEs for Effect on Weight (Safety Analysis Set)
CT-8.9.8	Incidence of TEAEs for Haematopoietic/Leukopenia (Safety Analysis Set)
CT-8.9.9	Incidence of TEAEs for Hypersensitivity (Safety Analysis Set)
CT-8.9.10	Incidence of TEAEs for Neuroleptic Malignant Syndrome (Safety Analysis Set)
CT-8.9.11	Incidence of TEAEs for Orthostatic Hypotension, Dizziness, and Syncope (Safety Analysis Set)
CT-8.9.12	Incidence of TEAEs for Effect on Prolactin (Safety Analysis Set)
CT-8.9.13	Incidence of TEAEs for QT Prolongation (Safety Analysis Set)
CT-8.9.14	Incidence of TEAEs for Rhabdomyolysis and CPK Elevation (Safety Analysis Set)
CT-8.9.15	Incidence of TEAEs for Seizures (Safety Analysis Set)
CT-8.9.16	Incidence of TEAEs for Somnolence (Safety Analysis Set)
CT-8.9.17	Incidence of TEAEs for Suicidality (Safety Analysis Set)
CT-8.9.18	Incidence of TEAEs for VTE (Thrombotic and Embolic Events) (Safety Analysis Set)
CT-8.9.19	Incidence of TEAEs for Pneumonia (Safety Analysis Set)
CT-8.10.1	Incidence of TEAEs by MedDRA System Organ Class and Preferred Term by Medical Care Category (Safety Analysis Set)
CT-8.10.2	Incidence of TEAEs by MedDRA System Organ Class and Preferred Term by Prior Antipsychotics (Safety Analysis Set)

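### The Appendix 4 cardiovascular list leaves out Cardiac arrest and Cardiac death, so table CT-8.9.4 and listing CT-9.4.4 can undercount cardiac collapse

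*SAP*

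**What the plan says.** SAP section 9.2.1 names 19 groups of adverse events of interest, one of them "Cardiovascular AEs", and states that "Each AE of interest is defined in Appendix 4". For each group it plans counts and percentages of subjects by system organ class and preferred term, for each arm and for brexpiprazole overall. No test, threshold or decision is attached. In Appendix 5 the cardiovascular group feeds table CT-8.9.4 and listing CT-9.4.4; the QT prolongation group feeds CT-8.9.13 and CT-9.4.13.

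The cardiovascular list in Appendix 4 runs alphabetically from "Accelerated idioventricular rhythm" to Wolff-Parkinson-White syndrome congenital. "Cardiac arrest", Cardiac death and Sudden death are in Appendix 4 only under QT prolongation.

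Protocol section 2.1 explains the exclusion criteria and the independent data monitoring committee by reference to cerebrovascular disorder, "cardiac disorder, pneumonia, and other infections, which were the causes of death associated with atypical antipsychotics".

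**The concern.** CT-8.9.4 is where a reader will look for the cardiac safety of a drug whose class carries a cardiac mortality signal that the protocol itself cites. A cardiac grouping that takes in pulseless electrical activity and asystole but not cardiac arrest or cardiac death has no evident principle behind it. The same clinical event, described in different words by two sites, could be counted for one subject and not for the other. Such events are likely to be few, so a single uncounted one can alter the comparison between arms in that table.

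**Working it through.** No figure in the plan has to be reproduced. The check is one of list membership.

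**1. Which list is the cardiovascular one.** The readable text shows no heading over this block. Section 9.2.1 names 19 groups and Appendix 5 has 19 matching tables (CT-8.9.1 to CT-8.9.19), while 18 headings are readable in Appendix 4. The one block left over lies between the accident/injury terms and the cerebrovascular terms, and its content is cardiac. The missing heading is an artefact of the text and is not criticised.

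**2. What stands where each term would sort.**

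| Term | Neighbours in the cardiovascular list | Page footer in the gap? | Conclusion |
|---|---|---|---|
| Cardiac arrest | Bundle branch block right, then Cardiac asthma | No | Absent |
| Cardiac death | Cardiac asthma, then Cardiac failure | No | Absent |
| Sudden death | Sudden cardiac death, then Supraventricular extrasystoles | No | Absent |
| Cardio-respiratory arrest | Cardiac ventricular scarring, then Cardiogenic shock | Yes | Not seen; needs checking |

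The last position rests on the Appendix sorting hyphens ahead of letters: its B-lymphocyte terms come before Babesiosis.

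**3. Could the aim have been to avoid listing a term twice?** The QT prolongation list has 23 terms. Of these, 16 are also in the cardiovascular list (for example Torsade de pointes, Ventricular fibrillation and Sudden cardiac death). That leaves 23 − 16 = 7 not seen there: Cardiac arrest, Cardiac death, Cardio-respiratory arrest, Sudden death, Electrocardiogram QT interval abnormal, Loss of consciousness and Syncope. Overlap is the rule, so avoiding it does not explain the gap.

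**4. Could the list have been kept narrow on purpose?** It includes Infarction and Foetal arrhythmia, so narrowness does not explain the gap either.

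**5. What happens to one subject, by code.**

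| Only event coded as | CT-8.9.4 and CT-9.4.4 | QT outputs (CT-8.9.13, CT-9.4.13) | Overall TEAE table (CT-8.2.1) |
|---|---|---|---|
| Pulseless electrical activity | Yes | No | Yes |
| Ventricular fibrillation | Yes | Yes | Yes |
| Cardiac arrest | **No** | Yes | Yes |
| Cardiac death | **No** | Yes | Yes |

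A life-threatening or fatal event is serious under Protocol section 5.1, so it also enters CT-8.5.1 and listing CT-9.2. If fatal, it enters CT-8.4.1 and listing CT-9.1.

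**6. Size.** One uncounted subject in a planned arm of 148 is 1/148 = 0.0068, or 0.7%. The documents give no expected rate for these events, so nothing further can be derived.

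**The case against.** The strongest reply is that nothing is lost. An arrest shows up in the overall, serious and QT outputs and, when fatal, in the death outputs, and CT-8.9.4 is purely descriptive. The list also catches many grave events, among them Acute myocardial infarction, Cardiogenic shock, Ventricular fibrillation and Sudden cardiac death. All of that stands. A reader might infer from the omission that the cardiovascular table misses fatal cardiac events generally, or that such events vanish from the report; the documents support neither. What remains is that the grouped cardiovascular figure is incomplete for the omitted terms, and the other outputs do not correct that figure.

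Three further inferences are tempting and should not be drawn.

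- **That "Cardio-respiratory arrest" is also proven missing.** A page footer falls exactly where it would sort, so its absence from the readable text is not conclusive.
- **That "Blood creatine phosphokinase increased" and its abnormal counterpart do not belong.** They sit beside the MB-fraction terms, and the list also holds troponin terms. The laboratory panel in Protocol Table 3.8.3.2-1 measures CPK but neither CK-MB nor troponin, so keeping total CPK is a defensible, sensitive choice. Under Protocol section 5.1 a laboratory value becomes an adverse event only if it is judged medically relevant, leads to discontinuation or is serious. The table shows each preferred term, so a reader can set CPK aside. Listing these terms under neuroleptic malignant syndrome and rhabdomyolysis as well is ordinary overlap for this Appendix.
- **That Tachycardia ought to be added.** The list already has the sinus, atrial, supraventricular and ventricular forms. Adding the unspecific term is a matter of preference.

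**Conclusion.** The point holds in a limited form. The cardiovascular list omits Cardiac arrest and Cardiac death, and also the less specific Sudden death, while including close equivalents. As written, CT-8.9.4 and CT-9.4.4 would leave out a subject whose only event is coded to one of those terms. This is a misclassification that can undercount in one descriptive table and its listing. It does not touch efficacy, the overall adverse event tables or the reporting of deaths. One event is 0.7% of a 148-subject arm; how many events would be affected cannot be said.

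The conclusion assumes that the unheaded block is the cardiovascular list, which follows by elimination, and that no lines were dropped inside the alphabetical runs around the three terms, of which there is no sign. It is worth correcting because the protocol singles out cardiac causes of death and the correction is cheap.

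**What to change.** In Appendix 4, add Cardiac arrest and Cardiac death to the cardiovascular category. Check the source Appendix for Cardio-respiratory arrest and add it if it is absent. Consider Sudden death, and record the decision either way, since it is less specific. Leave all these terms under QT prolongation as well.

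Produce CT-8.9.4 and CT-9.4.4 on the revised list, with a note on how it differs from any other programme tables that use the present list (the documents do not say whether there are any). Record the change in SAP section 15. Leave Tachycardia and the CPK terms as they are; at most, add a footnote that non-MB CPK terms are included and can be read off by preferred term.

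The cost is two to four entries in one lookup list and one run each of a table and a listing. The only real drawback is some loss of comparability with tables built on the present list, which the note addresses.

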9.2.2 Subgroup Analysis of Adverse Events

Numbers and proportions of subjects with TEAEs will be summarized by SOC and PT in each of the following subgroups, for each treatment group and for the overall brexpiprazole group.

- Medical care category (inpatient, outpatient)
- Prior use of antipsychotics (yes or no)
- Type of caregiver (hospital staff, care facility staff, family, or other)
- Sex (male, female)
- Age $(< 80, \ge 80)$ $(< 65, \ge 65 \text{ to } < 75, \ge 75)$
- Body weight (\leq median, > median)
- BMI (\leq median, > median)

- CYP2D6 phenotype (IM, EM, PM, Unknown)
- Impact of COVID-19 pandemic (subjects who completed/discontinued the trial before 07 Apr 2020, subjects who completed/discontinued the trial on or after 07 Apr 2020)
- Concomitant use of antidementia drugs (yes or no)

9.3 Clinical Laboratory Data

For each quantitative laboratory parameter, descriptive statistics of actual measurements and changes from baseline at each time point and the last time point will be calculated for each treatment group and for the overall brexpiprazole group.

For each quantitative laboratory parameter, actual measurements will be classified as "lower than the lower limit of the reference range," "within the reference range," and "higher than the upper limit of the reference range" using the reference range specified by the central laboratory, and a shift table from baseline will be produced for each treatment group and for the overall brexpiprazole group.

For each qualitative laboratory parameter, a shift table from baseline will be produced for each treatment group and for the overall brexpiprazole group.

Numbers and proportions of subjects with laboratory test values not meeting the criteria for potentially clinically significant laboratory test values (Appendix 2) at baseline and meeting the criteria after treatment will be determined for each treatment group and for the overall brexpiprazole group. A listing of these subjects will be provided.

Numbers and proportions of subjects with postdose values of alanine aminotransferase (ALT), aspartate aminotransferase (AST), and total bilirubin (TBL) meeting Hy's Law criteria (ALT or AST \geq 3 × the upper limit of normal [ULN] and TBL \geq 2 × ULN) will be determined for each treatment group and for the overall brexpiprazole group. A listing of these subjects will be provided.

Numbers and proportions of subjects with a prolactin value not meeting the criteria of $> 1 \times ULN$, $> 2 \times ULN$, or $> 3 \times ULN$ at baseline and meeting the criteria after treatment will be determined by sex for each treatment group and for the overall brexpiprazole group. A listing of these subjects will be provided.

Numbers and proportions of subjects with postdose values of fasting low-density lipoprotein (LDL) cholesterol, high-density lipoprotein (HDL) cholesterol, triglyceride, and blood glucose meeting the criteria for changes in glucose and lipid metabolism-related parameters (Table 9.3-1) will be determined by baseline value for each treatment group and for the overall brexpiprazole group. A listing of these subjects will be provided.

Table 9.3-1 C	hanges in Glucose and Lipi	d Metabolism-related
Parameters		
LAB PARAMETER	BASELINE	ANYTIME POST BASELINE
Cholesterol, Fasting	Normal <200	High >=240
(mg/dL)	Borderline 200-<240	High >=240
	Normal/Borderline <240	High >=240
	Normal <200	Borderline/High >=200
	Any Value	Increased >=40
LDL Cholesterol, Fasting	Normal <100	High >=160
(mg/dL)	Borderline 100-<160	High >=160
	Normal/Borderline < 160	High >=160
	Normal <100	Borderline/High >=100
	Any Value	Increased >=30
HDL Cholesterol, Fasting	Normal >=40	Low <40
(mg/dL)	Any Value	Decreased >=20
Triglycerides, Fasting	Normal <150	High 200-<500
(mg/dL)	Normal <150	Very High >=500
	Borderline 150-<200	High 200-<500
	Normal/Borderline < 200	High 200-<500
	Normal/Borderline < 200	Very High >=500
	Normal <150	Borderline/High/Very High >=150
	Normal/Borderline/high <500	Very High >=500
	Any Value	Increased >=50
Glucose Fasting, Serum	Normal <100	High >=126
(mg/dL)	Impaired 100-<126	High >=126
	Normal/Impaired <126	High >=126
	Any Value	Increased >=10

